## **9.8 STUDY DRUG EXPOSURE AND DOSING**

### **9.8.1 EXPOSURE TO STUDY DRUG**

Extent of treatment exposure will be summarized for JTX-2011 and JTX-2011 and nivolumab /or ipilimumab /or pembrolizumab as follows:

- Total Exposure (weeks) derived as (last dose date – first dose date + 1)/7
- Number and percentage of patients beginning 1, 2, 3, ...., 6 and > 6 cycles [Actual dose groups] and number of cycles started summarized as a continuous variable
- Total actual cumulative dose (mg/kg) received overall and by cycle, where total actual dose is the summation of each dose as collected on the eCRF

### **9.8.2 SUMMARIZATION OF DOSE INTERRUPTIONS AND DOSE MODIFICATIONS**

A dose reduction is defined as when the actual dose administered is less than the prescribed dose (within 10% is not considered a reduction) on any given day for any reason with the exception of a day where the total dose administered is 0 mg as this is not considered a dose reduction.

A dose interruptions/delay/missed dose is defined as a planned dosing day with 0 mg administered.

Subjects will be summarized by total number of doses, subject frequency of doses and percentage according to:

- Patients with at least one dose reduction overall and by cycle.
- Patients with at least one dose interruption overall and by cycle

Subjects having a dose interruption or dose reduction due to an adverse event will be listed.

### **9.8.3 DOSE INTENSITY SUMMARIZATION**

Study drug administration will be summarized as follows: Number of doses received, cumulative dose in mg, treatment duration in weeks, dose intensity in mg/week and relative dose intensity (%).

Dose intensity (mg/week) and relative dose intensity (%) is calculated as follows

$$\text{Dose Intensity (mg/week)} = \frac{\text{Cumulative Dose (mg)}}{\text{Treatment Duration (weeks)}}$$

$$\text{Relative Dose Intensity (\%)} = \frac{100 * \text{Dose Intensity (mg/week)}}{\text{Planned Dose Intensity (mg/week)}}$$

where

$$\text{Planned Dose Intensity} = \frac{\text{Planned Dose (mg) per cycle} * \text{total \# cycles}}{(\text{Planned days in cycles} * \text{total \# cycles}) / 7}$$

Data will be provided in subject listings.

## 9.9 SAFETY ANALYSES

The safety analysis will include the evaluation of the following data:

- Adverse events (AEs)
- Laboratory results
- Vital signs: pulse rate, systolic and diastolic blood pressure
- Electrocardiograms (ECGs)
- Physical exams
- ECOG

All safety parameters will be summarized descriptively. The SAF will be used for displaying safety outputs unless otherwise specified. Subsets of the safety set may be presented separately. Data will be provided in subject listings.

### 9.9.1 ADVERSE EVENTS

Adverse events (AEs) will be listed and summarized using MedDRA v19 coded terms. Listings will be created by categories for AEs as outlined below:

- All adverse events (AEs) with flags for treatment emergent adverse events (TEAEs) and flags of relatedness to study drug(s)
- SAEs with flags for treatment emergent adverse events (TEAEs) and flags of relatedness to study drug(s)
- Immune related adverse events (irAEs)
- Infusion related reactions (IRRs)
- TEAEs leading to death
- TEAEs leading to study drug interruption, reduction, hold or permanent study drug discontinuation
- TEAEs considered as DLTs

A general overview summary table will include frequencies by category of AE (as listed above) and will also include TEAE by severity grade and relationship to study drug (both JTX-2011 and/or nivolumab and/or ipilimumab and/or pembrolizumab).

Frequencies and percentages will be reported by System Organ Class (SOC) and Preferred Term (PT). Patients with multiple events for a category will be counted once in the highest CTCAE classification. Summary tables will include treatment-emergent AEs, unless specified otherwise. Missing onset date for an event will be considered as TEAE. If relatedness is missing the adverse event will be considered related. The denominator (N) for adverse events reported at each cycle will include SAF patients who are dosed at least once in that cycle. Important note: Patients will be counted in terms of number and adverse event in the actual dose group as received, not the as intended dose group. Summary tables by SOC and PT will be sorted in descending frequency of SOC for the total column, then in descending frequency of PT within SOC for the total column. Summary tables by PT will be sorted in descending frequency of PT for the total column.

The following summary TEAE tables listed in Table 7 below will be presented for Phase 1 and Phase 2 parts. In addition, DLTs will be summarized by SOC and PT only for Phase 1 parts (A, B, E, G) for DLT Evaluable Set.

Table 7 Summary of Adverse Event Displays

Category	TEAE	IRR	irAE	TEAE Related to JTX2011	TEAE Related to Any Study Drug	Serious TEAE	Related SAE	TEAE Resulting in Death	TEAE Resulting in Dose Interruption, Reduction or Hold	TEAE Resulting in Study Drug Discontinuation
SOC and PT	X			X	X	X	X			
SOC/PT/Max. Grade	X			X	X					
SOC/PT/Max. Grade $\geq 3$				X						
SOC/PT by Cycle	X									
SOC/PT by Grade, Cycle										

Category	TEAE	IRR	irAE	TEAE Related to JTX2011	TEAE Related to Any Study Drug	Serious TEAE	Related SAE	TEAE Resulting in Death	TEAE Resulting in Dose Interruption, Reduction or Hold	TEAE Resulting in Study Drug Discontinuation
PT	X	X	X	X		X	X	X	X	X
PT and Cycle		X	X							

A patient having multiple events within a system organ class is counted only once for that SOC. Similarly, a patient having multiple events under a preferred term is counted only once for that PT.

#### 9.9.2 LABORATORY DATA

Laboratory parameters will be analyzed using categorical summaries.

Categorical analysis of laboratory tests using observed data includes summarizing laboratory abnormalities considered clinically significant and treatment-emergent. The following defines this group;

- Abnormality satisfies current criteria and occurs first time while the patient is on study treatment (i.e., not seen prior to treatment).
- Abnormality satisfies the current criteria of abnormality, was observed prior to start of treatment, and worsened during study treatment.

The number of patients evaluable for laboratory abnormalities must have at least one observation for at least one test while on treatment. While the number of patients evaluable for clinically significant laboratory abnormalities (includes lab TEAEs) is the number of patients with a clinically significant abnormality for at least one laboratory test while on treatment.

Additional summaries will be produced overall by Maximum CTCAE grade. Frequencies and percentages in each grade and overall will be presented.

Shift in laboratory analyte grade will be characterized by worst on-study CTCAE grade to end of treatment. Shift categories from baseline will be selecting the maximum CTCAE grade for each patient during the study compared to baseline. Grades that are not part of CTCAE grading will be blank. Percentages will be based on the number of patients with non-missing baseline and postbaseline values per each analyte.

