9.1.1. Safety Endpoints

The following safety endpoints will be assessed:

- Incidence and severity of treatment-emergent adverse events;
- Incidence and severity of treatment-emergent changes in clinical laboratory values;
- Incidence of dose limiting toxicities;
- Incidence of anti-drug antibodies to JTX-2011 and/or nivolumab, ipilimumab, or pembrolizumab;
- Incidence of neutralizing antibodies to JTX-2011 and/or nivolumab, ipilimumab, or pembrolizumab;
- Incidence of decreases in ECOG performance status;
- Incidence of clinically significant changes in ECG measurements.

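### SAP 9.9.2 words the evaluable count for clinically significant laboratory abnormalities as the count of affected patients; the percentage base needs correcting

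*SAP*

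**What the plan says.** SAP 9.9.2 plans a categorical summary of laboratory abnormalities that are clinically significant and treatment-emergent. An abnormality qualifies if it first appears on treatment, or if it was present before treatment and then worsened.

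Two consecutive sentences then state who is evaluable:

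- For laboratory abnormalities in general, patients "must have at least one observation for at least one test while on treatment".
- For clinically significant laboratory abnormalities, including those reported as treatment-emergent adverse events, the evaluable number "is the number of patients with a clinically significant abnormality for at least one laboratory test while on treatment".

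A separate paragraph introduces summaries by maximum CTCAE grade. The last paragraph describes grade shifts and ends: "Percentages will be based on the number of patients with non-missing baseline and postbaseline values per each analyte".

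The opening of SAP 9.9 sets the general default: "The SAF will be used for displaying safety outputs unless otherwise specified". Protocol 9.1.1 lists the endpoint that these tables serve: "Incidence and severity of treatment-emergent changes in clinical laboratory values".

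**The concern.** The first evaluable count depends only on whether a patient was tested on treatment. The second depends on the result. If the second is used as the base of a percentage, numerator and denominator are the same patients for the any-test row. For a single analyte, the figure becomes the share of affected patients who had that particular abnormality. Neither is an incidence, which is what the protocol endpoint asks for.

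SAP 7.2 arranges summaries by dose level in Phase 1 and by tumor cohort in Phase 2. Percentages built on a base selected by outcome cannot be compared across those columns, because the base shrinks or grows with the number of events.

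**Working it through.** The SAP attaches no figure to this definition, so there is nothing to reproduce. The check has two parts: whether the evaluable count would serve as a base, and what follows if it does.

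**Does evaluable mean the base?** Section 9.9.2 does not say so, so this is an inference. Three things support it:

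- SAP 8.3.2 (ORR) and 8.3.9 (irORR) define the rate relative to the evaluable subjects. SAP 8.3.5.1 and 8.3.7.1 (landmark PFS and OS) put the count over the subjects considered evaluable.
- The sentence immediately before the disputed one uses the word for the tested, at-risk group.
- SAP 7.2 has percentages shown for every frequency above zero, so this table needs a base, and 9.9.2 gives no other for it in plain terms.

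**Does anything else supply the base?**

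- The Safety Analysis Set is only the default where nothing else is specified, and 9.9.2 specifies its own counts.
- The non-missing baseline and post-baseline rule closes the shift paragraph. The maximum-grade paragraph stands between it and the clinically significant summary, so its reach is at best unclear.
- Protocol 9.4.8.2 says each patient is counted once for outliers but names no denominator.

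**Arithmetic.** Let N be the patients with at least one on-treatment laboratory observation, x the patients with at least one clinically significant abnormality, and k the patients with that abnormality on one given analyte.

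- Any test: as written, x/x; on the SAP's first evaluable definition, x/N.
- One analyte: as written, k/x; on a tested base, k/N (assuming all N were tested for that analyte).

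Take N = 15, the approximate Part C and D cohort size in SAP section 5. The values of x and k are assumed.

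| x | As written, x/x | Tested base, x/15 |
|---|---|---|
| 1 | 100% | 6.7% |
| 3 | 100% | 20.0% |
| 5 | 100% | 33.3% |
| 10 | 100% | 66.7% |

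For x = 0 the expression is 0/0.

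| k | x | As written, k/x | Tested base, k/15 |
|---|---|---|---|
| 1 | 3 | 33.3% | 6.7% |
| 2 | 3 | 66.7% | 13.3% |
| 3 | 5 | 60.0% | 20.0% |

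Read the last two rows as two cohorts. The tested base puts the second cohort higher (20.0% against 13.3%), while the literal base puts it lower (60.0% against 66.7%). The comparison between columns can therefore reverse.

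**The case against.** The best defence is that the sentence is a slip of wording. The SAP names denominators openly elsewhere: for adverse events by cycle in 9.9.1, for response rates in 7.12.1 and 9.11.1, and for percentages at the end of 9.9.2. It attaches no such term to this count. Its use of evaluable is also not uniform: 9.11.1 keeps patients classed as non-evaluable for best response in the denominator. Read as a pair, the two sentences could be giving first the base and then the number affected, with only the word evaluable misplaced. A row fixed at 100% would probably be noticed when the mock shells or outputs are reviewed. This stands as a reason for restraint: the documents do not show that the final table will be wrong. It does not remove the need for correction, because a programmer following the text literally would produce the wrong base.

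It can also be said that the closing percentage rule covers the whole section. Its position makes that possible but not clear.

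A reader might go further and infer that the trial's main laboratory safety evidence is compromised. The documents do not support that. Safety is a primary objective, but laboratory values are one of several safety endpoints in SAP 3.2.1, and nothing singles this summary out as a primary display. The maximum-grade and shift summaries serve the same protocol endpoint without this definition. Laboratory events recorded as adverse events also appear in the tables by SOC and preferred term. That overlap is partial, because Protocol 8.14.6 limits laboratory adverse events to those with intervention or symptoms.

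**Conclusion.** The point holds as a wording error with a real consequence if followed literally. The evaluable count for clinically significant laboratory abnormalities is stated as the affected count, and no other text clearly repairs it. If it is used as the percentage base, the any-test incidence is 100% for any x of 1 or more, and per-analyte figures are shares of affected patients. In the illustration, rates from 6.7% to 66.7% would all show as 100%.

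The conclusion rests on reading evaluable as the base, which is the natural reading but not an explicit one. The sizes rest on assumed event counts and a planned cohort size. It would be too strong to say that the SAP defines this denominator outright or that inflated percentages are certain. The effect is confined to one descriptive safety summary; no hypothesis test, sample size or dose rule depends on it. It should be corrected before the tables are programmed.

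**What to change.** Keep the affected count and relabel it as the numerator; deleting it would remove the only statement of the any-test number affected. Then state the bases:

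- **Overall:** patients with at least one on-treatment laboratory value, which is the SAP's own first definition.
- **Per analyte:** patients with at least one on-treatment value of that analyte.
- **Baseline:** also require a baseline value of the analyte wherever treatment-emergence or worsening is judged against baseline, and say how patients without one are shown.

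It would help to say, in the same edit, whether the closing percentage rule in 9.9.2 applies to the shift tables only. The cost is one or two SAP sentences and a matching shell footnote, with no new data and no effect on other analyses.

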#### 9.9.3 VITAL SIGNS

Vital sign parameters: systolic and diastolic blood pressure (mmHg), respiratory rate (breaths per minute), body temperature (C°), weight (kg) and pulse rate (beats per minute)

will be summarized by observed and change from baseline according to minimum and maximum values. Frequency and percentage of patients for each observed parameter outside the normal range during treatment (up to 30 days post last dose date) will be reported. Data will be listed

Table 8     Summary of Vital Signs

Parameter	Units	Normal Range
Systolic Blood Pressure	mmHg	90 - 120
Diastolic Blood Pressure	mmHg	60 - 80
Pulse Rate	Beats per minute	60-100
Respiratory Rate	Breaths per minute	12 – 20

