1.6. Adverse Events

1.6.1. JTX-2011 Monotherapy

Based on the preclinical toxicology and observations thus far in this trial, JTX-2011 does not appear to cause spontaneous activation of the immune system nor does it induce pro-inflammatory cytokines at levels likely to induce cytokine storm, so the risk of acute

inflammatory reactions due to cytokine induction is predicted to be low. However, JTX-2011 may cause signs and symptoms of an infusion reaction or cytokine storm which may include the following: headache, fever, facial flushing, pruritus, myalgia, nausea, chest tightness, dyspnea, vomiting, erythema, abdominal discomfort, diaphoresis, shivers, hypertension, hypotension, lightheadedness, palpitations, and urticaria.

Subjects will be observed for at least 1 hour after completion of JTX-2011 infusion for assessment of IV infusion tolerability.

JTX-2011 may be expected to cause adverse events similar to other immunotherapy agents, with immune-related toxicities caused by immune stimulation in organs not involved by cancer. As such, immune-related adverse events which can involve any organ system may be seen. These include pneumonitis, colitis, hepatitis, endocrinopathies, nephritis, rash, and encephalitis (Opdivo® Full Prescribing Information {Bristol-Myers Squibb Company 2017a}).

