9.4.8.2. Clinical Laboratory Evaluation

Clinical laboratory values will be evaluated for each laboratory parameter by subject. Abnormal laboratory values will be identified as those outside (above or below) the normal range. Reference (normal) ranges for laboratory parameters will be included in the Clinical Study Report for this protocol.

Descriptive summary statistics (mean, standard deviation, median and range) of the laboratory parameters will be evaluated for hematology and biochemistry. Categorical values will be summarized using number of observations and percentages (urinalysis assessment).

Laboratory test results will be assigned an LNH classification according to whether the value was below (L), within (N), or above (H) the laboratory reference range. Summary data of LNH will be provided by the worst category and by the shift from baseline to the worst. In addition, the CTCAE grading system will be implemented to safety laboratory values. The resulted grades of laboratory assessments will be summarized as categorical data.

Clinical laboratory results will also be evaluated using outlier criteria (potentially clinically important per investigator's discretion). For the incidence of outliers, each patient will be counted only once in the laboratory parameter value high and low categories, as applicable.

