9.4.8.3. Vital Signs

Vital sign values (BP, T, HR, RR, and SpO₂), and weight will be evaluated on an individual basis by patient. Abnormal vital sign values will be identified as those outside (above or below) the reference range. Descriptive summary statistics (mean, standard deviation, median, and range) for vital sign parameters will be tabulated.

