# 7. GENERAL CONSIDERATIONS AND DATA HANDLING CONVENTIONS

## 7.1 FORMAT AND DISPLAY

All statistical analyses discussed in this SAP will be generated for the final CSR. All datasets, documentation, and the SAP will be archived in the Trial Master File (TMF). Tables, figures, and listings (TFLs), as described in this document and in the mock shells, will be created using SAS version 9.4 or higher. Mock table, listing, and figure shells will be developed for detailed presentation purposes. The mock tables, listings, and figure shells will not be considered as part of the SAP signoff.

TFL layout will be landscape. Margins will be a minimum as such: top 3/8 inch, bottom 3/8 inch, right 3/8 inch, and left 3/4 inch. Font will be a non-proportional courier new 8 or 9 pt font. Headers will include program name, associated project, and raw EDC data cut. Titles will generally have lines for Table/Figure/Appendix (i.e., Listing) with a number. Titles will include TFL numbers, where tables start with 14, listings with 16,

and figures with 14. Additional lines will include an appropriate title and study population for the output. All footnotes will be ordered by abbreviations, notes, and superscripted footnotes [1], [2], [3], etc. Report creation date and significant program modifications and date are documented in the SAS programs. At the bottom of each page a reference to the source data and the path of the program that created the TFL will be displayed. In some database systems, it is useful to extract a subset of data for use in the production of tables. The date of extraction printed will be the latest date upon which the extraction of contributing data occurred; which in some cases can come from multiple datasets.

"Source data" refers to the data listings of SDTM or ADaM data appropriate for the TFL.

Database lock will be performed when all EDC and external data have been cleaned. The final database lock date will be considered the date of the final extraction dataset date (EDC or external).

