## **8. ENDPOINT DEFINITIONS AND DERIVATIONS**

### **8.1 SAFETY DEFINITIONS AND ENDPOINTS**

#### **8.1.1 ADVERSE EVENT ENDPOINTS**

Adverse events will be categorized by pre-existing, treatment emergent and post treatment.

- Pre-existing AEs are designated to events that occur prior to the first dose of study drug(s) or observed prior to first dose but did not increase in NCI CTCAE toxicity grade during treatment period.
- Post-treatment adverse events will be any adverse events reported outside the 28 day post dose treatment window until the end of study participation. Any subsequent non-protocol treatment for the cancer diagnosis will end the potential study drug(s) adverse event data collection.
- Treatment-Emergent Adverse Events (TEAEs) are designated to events that occur after the start of study drug(s) and on or before 28 days after final dose of study drug, and were not observed prior to start of treatment; Or if the event was observed prior to the start of study drug but increased in NCI CTCAE grade after either the start of study drug or prior to 28 days after the final dose of study drug. Pre-existing adverse events may be reclassified as TEAEs if the frequency of the event increases during treatment.
- Treatment Related TEAEs will include those TEAEs which are possibly or probably related to study drug(s) as designated by the investigator. Events having a missing relatedness will be designated as definitely related on tables but the listing will display the data as collected. Relationship may be attributed by JTX-2011 and/or nivolumab/ipilimumab/pembrolizumab and will be displayed separately.
- Serious adverse events (SAEs) will include all events classified as serious on the eCRF. The electronic database used to enter data at the site (i.e., RAVE / iMedidata) will be deemed as the complete report for adverse event information. The pharmacovigilance database will be reconciled against the EDC.

- Infusion related reactions (IRRs) may be captured as an adverse event as well as the symptoms that cause the IRR. Symptoms of IRRs are events occurring shortly after or during the study drug infusion. Symptoms may include but are not limited to: flushing, headache, nausea, fever, chills, dyspnea, rash, hypotension, wheezing, coughing, tachycardia. Any sign/symptom determined to be associated with an IRR may be counted as such in adverse event reporting. The highest grade sign/symptom must be associated with the IRR preferred term.

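### The blood pressure abnormality count in SAP 9.9.3 does not separate low from high, so this one display responds weakly to new hypotension.

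*SAP*

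**What the plan says.** SAP 9.9.3 plans two displays for vital signs, plus a listing.

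- **Summaries.** Each parameter "will be summarized by observed and change from baseline according to minimum and maximum values".
- **Count.** "Frequency and percentage of patients for each observed parameter outside the normal range during treatment (up to 30 days post last dose date"). Table 8 sets the limits: systolic 90-120 mmHg, diastolic 60-80 mmHg, pulse 60-100, respiratory rate 12-20.

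The count has neither a low/high split nor a baseline condition. Protocol 9.4.8.3 adds neither: "Abnormal vital sign values will be identified as those outside (above or below) the reference range".

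The laboratory rules go further. Protocol 9.4.8.2 classes results as low, normal or high and states: "Summary data of LNH will be provided by the worst category and by the shift from baseline to the worst". SAP 9.9.2 covers an abnormality that is new on treatment ("Abnormality satisfies current criteria and occurs first time while the patient is on study treatment (i.e., not seen prior to treatment") and also one seen before treatment that worsened.

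A table shell could split the vital sign count, but SAP 7.1 says: "The mock tables, listings, and figure shells will not be considered as part of the SAP signoff".

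**The concern.** Hypotension is the low-side event of interest. Protocol 1.6.1 lists it among signs of an infusion reaction or cytokine storm ("erythema, abdominal discomfort, diaphoresis, shivers, hypertension, hypotension, lightheadedness, palpitations, and urticaria"), and SAP 8.1.1 lists it among infusion reaction symptoms.

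The SAP 9.9.3 count is the only threshold count planned for vital signs. A patient enters it once, on any out-of-range reading. Vital signs are taken before and at the end of each JTX-2011 infusion, so each patient has many chances to exceed 120 systolic or 80 diastolic. Once that has happened, a later reading below 90 leaves the count unchanged. A reader who took this row as the summary of blood pressure safety could see little movement when new hypotension occurs.

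**Working it through.** The plan gives no figure for this count, so there is none to reproduce. The check asks how far the stated rule moves when low readings are added.

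**Inputs from the documents.** The Table 8 limits; the rule that any on-treatment reading counts; repeated readings per patient (schedules of events, Protocol Appendix 1).

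**Inputs assumed.** Systolic pressure is normal between and within patients: mean 115, 118, 120, 125 or 130; between-patient SD 10, 12 or 15; within-patient SD *s* 6, 8 or 10; *k* = 4, 8 or 12 on-treatment readings; one baseline reading. That is 5 × 3 × 3 × 3 = 135 settings.

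**Step 1. The count with no drug effect.** For a patient with true mean μ,

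P = 1 − E[{Φ((120 − μ)/s) − Φ((90 − μ)/s)}^k].

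Over the grid P runs from 58% to 99.5%, median 89%. For diastolic pressure (means 70-78, SD 7-10 between and 5-7 within, 81 settings) it runs from 53% to 97%, median 83%.

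**Step 2. New hypotension in a random 10% of patients.** One reading below 90 adds a patient only if that patient is not yet counted:

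- Stated count: rise = 0.10 × (1 − P). At P = 58.3% this is 0.10 × 41.7 = 4.2 points. At P = 99.5% it is 0.10 × 0.5 = 0.05 points. The median is about 1.1.
- Low-side count: rise = 0.10 × (1 − P_low), where P_low = 1 − E[{1 − Φ((90 − μ)/s)}^k]. This gives 7.1 to 10.0 points, median 9.3.
- Low-side count restricted to patients not low at baseline: 7.0 to 10.0 points, median 9.3.

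The two low-side counts rise almost equally, so direction restores the response and the baseline condition does not.

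**Step 3. Hypotension in patients with low pressure to begin with.** If the 10% come from the lowest third of true systolic pressure, the stated count rises 0.2 to 8.2 points (median 3.1) and the new-low count 2.0 to 10.0 (median 7.9). The gap narrows, but the new-low count rises more in 134 of 135 settings.

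**Step 4. Which change helps on the low side.** This uses a second assumed grid: systolic mean 110-130 and diastolic mean 68-80, with SD 13/9 (also 10/7 and 16/11) and 8/6 between/within. Entries are the rise in points when 10% of patients have a new low reading.

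| Rule | Systolic | Diastolic |
|---|---|---|
| As written | 0.2-3.7 | 0.6-2.9 |
| Baseline condition alone | 0.2-3.3 | 0.6-2.4 |
| Upper limit 140/90 alone | 3.5-8.8 | 3.7-6.3 |
| Low side only | 6.7-10.0 | 4.5-9.3 |

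Direction contributes most and the upper limit helps. The baseline condition adds nothing.

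**Step 5. The high side.** On the first grid with no drug effect, 53% to 99% of patients have some systolic reading above 120. Requiring the value to be new still leaves 13% to 48%. Only 0% to 20% reach 160 or more, even with no baseline condition. Apportioning the gain on the second grid (140/90 as comparator) gives 3.3-5.1 points to the systolic limit and 0.2-3.1 to direction. For diastolic pressure the result depends on the mean: direction is larger at 68-70 (4.6 against 2.4 at 68 with five readings), the two are near equal at 72, and the limit is larger from 74 upward.

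**Step 6. A fall in everyone.** The range 90-120 has midpoint 105. A 20 mmHg fall at every reading moves a mean of 115 to 95; both are 10 mmHg from the midpoint, so the count is unchanged in those 27 settings. With means of 118 or more (4 × 27 = 108 settings) the new mean is closer to 105 and the count falls, by up to 47 points (median over all 135 settings about −9). If the fall affects only half of the readings, the count changes by −1.4 to +26 points (median +7), against +7 to +53 (median +32) for new-low.

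**Worked case, 15 patients.** Mean 125, SD 12 and 8, eight readings: P = 92.7%, so 15 × 0.927 = 13.9 patients are counted with no drug effect. A random 10% with new hypotension (1.5 patients) adds 1.5 × 0.073 = 0.1 patient. A low-side count, with P_low = 3.5%, adds 1.5 × 0.965 = 1.4.

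**The case against.** The strongest reply is that the signal is reported elsewhere. The sentence just before the count summarises observed values and change from baseline by minimum and maximum. The minimum and its change are directional and refer to baseline. Vital signs are listed. Hypotension reported as an event enters the adverse event and infusion reaction tables (SAP 9.9.1, Table 7); SAP 8.1.1 names it: "Symptoms may include but are not limited to: flushing, headache, nausea, fever, chills, dyspnea, rash, hypotension, wheezing, coughing, tachycardia". The Safety Monitoring Committee reviews vital signs at escalation (Protocol 6.1.1) and accumulating safety data about every three months afterwards (6.1.2). This stands, and it confines the point to one descriptive table.

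Second, the SAP is silent on direction; it does not say that low and high will be pooled, and a split is ordinary shell content. That is fair. However, the shells are outside the sign-off, so the signed plan does not secure the split.

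Third, every size above rests on assumed distributions and the ranges are wide. That also stands. What does not depend on them is the identity in Step 2: in a random subset, an undirected count can rise only among patients not already counted.

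A reader might infer that the count will improve when hypotension occurs. That needs a fall at nearly all readings in nearly everyone, which does not resemble an infusion reaction. With falls at half of the readings, the count usually rises.

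**Conclusion.** The point holds for this one count and is minor. As written, the systolic count is likely to include most patients before any drug effect (58% to 99.5% under the assumptions). It moves by about 0 to 4 points when a random 10% of patients have a new reading below 90, where a low-side count moves by about 7 to 10. If hypotension concentrates in patients with low pressure, the stated count can rise by up to about 8 points, and the contrast is smaller.

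The missing direction is the main cause, with help from the 120/80 limit. Three stronger readings are not supported:

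- **That the plan would miss hypotension.** The other displays and the committee review carry it, and the documents rest no decision on this table.
- **That the missing baseline condition causes the weak response.** Adding that condition alone brings no gain; it only shows that a value is new.
- **That the 120/80 limit is the main high-side problem throughout.** This holds for systolic pressure in every setting examined. For diastolic pressure it depends on the assumed mean.

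**What to change.** In SAP 9.9.3, report patients below the lower limit and patients above the upper limit separately, in one of two forms that the documents already use for laboratory data:

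- a baseline-to-worst low/normal/high shift, as in Protocol 9.4.8.2, with the lowest and highest on-treatment values shown separately because one patient can have both; or
- a count of values new or worsened from baseline, as in SAP 9.9.2, with worsening defined in the text.

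Either form keeps patients who were already abnormal and then worsened. Counting only patients within the limit at baseline would drop them.

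For blood pressure, add a higher upper cut-off chosen by the sponsor's medical reviewer. The 140/90 and 160 mmHg values above are illustrations, not values from the documents. The 30-day window can stay.

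Cost: SAP wording and one re-cut table. No new data are needed.
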